# 9.4.3 Analysis of the Secondary Endpoints

To assess the possible repair of chronically inflamed white matter lesions in which inflammation at the lesion edge has been modulated by tolebrutinib 120 mg/day, changes in T1 relaxation time within paramagnetic rim lesions, relative to non-rim lesions, will be determined by analysis of variance or mixedeffects models. Comparisons are relative to the scan taken just prior to initiation of 120 mg dosing. A threshold p-value of 0.025 will be taken as a significant change.

To assess the possible repair of chronically inflamed white matter lesions in which inflammation at the lesion edge has been modulated by tolebrutinib 120 mg/day, changes in size of paramagnetic rim lesions, relative to non-rim lesions, will be determined by analysis of variance or mixed-effects models. Comparisons are relative to the scan taken just prior to initiation of 120 mg dosing. A threshold p-value of 0.025

will be taken as a significant change.

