**Objectives:** *Primary Objective:* To evaluate the effects of 48 weeks of tolebrutinib 60 mg/day treatment on the paramagnetic rim of chronically inflamed white matter lesions, as seen on 7-tesla MRI.

Secondary Objectives: (1) To assess safety and tolerability of 48 weeks of treatment with tolebrutinib 60 mg and 96 weeks of treatment with tolebrutinib 120 mg (Cohort A) all following anti-CD20 antibody therapy. (2) To assess the possible repair of chronically inflamed white matter lesions in which inflammation at the lesion edge has been modulated by tolebrutinib.

**Endpoints**: *Primary Endpoint*: Per-patient proportion of lesions in which the paramagnetic rim has disappeared at the end of 48 weeks of tolebrutinib 60 mg.

Secondary Endpoints: (1) Adverse event tables. (2) Changes in T1 relaxation time within paramagnetic rim lesions at the end of 96 weeks of tolebrutinib 120 mg, relative to non-rim lesions. (3) Changes in size of paramagnetic rim lesions at the end of 96 weeks of tolebrutinib 120 mg, relative to non-rim lesions.

**Study Population:** Up to 10 adults with multiple sclerosis, targeting at least 7 participants who complete 48 weeks of therapy with tolebrutinib 60 mg in Cohort A. Up to 10 adults with multiple sclerosis who meet inclusion criteria but choose to stay on anti-CD20 therapy.

Phase: 2

[figure not shown]
**Description of Study Intervention:** Oral tolebrutinib 60 mg per day for 48 weeks (Initial Cohort), and a subgroup of patients already escalated to 120 mg (Cohort A), with optional long-term extension and follow-up.

**Study Duration:** 5 years

[figure not shown]
**Participant Duration:** 144 weeks (Cohort A) for primary and secondary outcomes, with optional long-term extension and follow-up.

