# **3** OBJECTIVES AND ENDPOINTS

OBJECTIVES	ENDPOINTS	JUSTIFICATION FOR ENDPOINTS					
Primary							
To evaluate the effects of 48 weeks of tolebrutinib 60 mg treatment on the paramag- netic rim of chronically in- flamed white matter lesions, as seen on 7-tesla MRI.	Per-participant proportion of lesions in which the paramagnetic rim has disappeared at the end of 48 weeks of tolebrutinib 60 mg treatment.	Paramagnetic rims indi- cate the presence of in- flammation and ongoing demyelination and axonal transection at the lesion edge. We have never ob- served complete disap- pearance of a chronic rim over the course of months, and the lesions under study will have been present for at least 6 months.					
Secondary							
To assess safety and tolera- bility of 96 weeks of tole- brutinib 60 mg (initial co- hort), or 48 weeks of treat- ment with tolebrutinib 60 mg and 96 weeks of treat- ment with tolebrutinib 120 mg (Cohort A), all follow- ing anti-CD20 antibody therapy.	Tabulation of adverse events.	There are no prior data regarding the specific combination of tolebru- tinib and anti-CD20 anti- bodies, or of BTK inhibi- tors and anti-CD20 anti- bodies in MS.					
To assess the possible repair of chronically inflamed white matter lesions in which in- flammation at the lesion edge has been modulated by tole- brutinib.	Changes in T1 relaxation time within paramagnetic rim lesions at the end of 96 weeks of tolebrutinib 120 mg, rela- tive to non-rim lesions. The analysis of T1 relaxation time changes will be per- formed by analysis of variance or mixed-effects models in study complet- ers. A threshold p-value of 0.025 will be taken as a significant change.	A reduction of the T1 relaxation time would be compatible with lesion repair.					
To assess the possible repair of chronically inflamed white matter lesions in which in- flammation at the lesion edge has been modulated by tole- brutinib.	Changes in size of paramagnetic rim lesions at the end of 96 weeks, relative to non-rim lesions. The analysis will be performed by analysis of variance or mixed-effects models in study com- pleters. A threshold p-value of 0.025 will be taken as a significant change.	A reduction in lesion size could indicate le- sion repair.					
Tertiary/Exploratory							

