# 9.2 SAMPLE SIZE DETERMINATION

Given our previous natural history data, which indicates that only 1 out of 29 individuals experienced subtle changes in at least one paramagnetic rim lesion over a period of  $\sim$ 5 years, we expect that very few to no participants in the non-tolebrutinib cohort will experience changes in this study and conservatively

estimate this null proportion to be 0.01. Although even a single tolebrutinib-cohort participant experiencing short-term changes would potentially be clinically meaningful, we have powered this study to detect disappearance of at least one paramagnetic rim lesion in 2 out of 7 completers (expected proportion: 0.29). In this scenario, the interval of (0.0367, 0.7096) will have 95% probability to include the true proportion. Thus, the null hypothesis will be rejected if 2 participants experience at least one lesion change.

To recruit 7 study completers in tolebrutinib Cohort A, we expected to enroll 10 prospective participants into that cohort. As of May 2023, the first 7 participants had completed 48 weeks of tolebrutinib 60 mg, so no additional participants will be recruited into this Cohort. Participants in the non-tolebrutinib comparison cohort (up to 10) will not be replaced if they drop out. We expect the total study duration, including the long-term extension (beyond Week 144 for Cohort A, to be approximately 5 years from the time of first dosing.

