# 9.3 POPULATIONS FOR ANALYSES

The analysis for the primary and MRI-based secondary outcomes will be performed on all study completers. The analysis for the safety and tolerability secondary outcome will be performed on all participants who take at least one dose of tolebrutinib. Populations for exploratory post-hoc analyses will be defined at a later date.

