# 9.4 STATISTICAL ANALYSES

9.4.1 General Approach

# 9.4.2 Analysis of the Primary Endpoint

The primary outcome is the per-patient proportion of lesions in which the paramagnetic rim has disappeared at the end of 48 weeks of tolebrutinib 60 mg/day, in comparison to the scan just prior to initiation of tolebrutinib dosing. Such participants can be in Cohort A or the Initial Cohort (combined analysis). Proportion of diminished/resolved paramagnetic rims is analyzed by investigators blinded to time point, reported descriptively, and compared to the assumption of no change off therapy via a binomial exact test. The analysis will be performed in study completers, and by definition no data will be missing. A threshold p-value of 0.05 will be taken as a significant change.

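### The 9.4.3 T1 and lesion-size tests can include at most 4 participants, Section 9 does not say so, related passages need reconciling, and the permitted models include one that can exceed its 0.025 level

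*Combined protocol and SAP*

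**What the plan says.** Section 9 states that there is no separate SAP, so it is the whole analysis plan. Section 9.4.3 compares change in T1 and in lesion size between rim and non-rim lesions, using either an ANOVA or a mixed-effects model, with a 0.025 threshold for each. For both endpoints: "Comparisons are relative to the scan taken just prior to initiation of 120 mg dosing". Section 9.1 states both hypotheses at the end of 96 weeks of 120 mg.

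The synopsis, 1.2, 1.3 and 6.1.2.1 report that 4 participants escalated to 120 mg and 3 stay at 60 mg. Section 6.1.2.5 records that further escalation was removed.

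Three sets of passages do not fit together:

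- **Population.** Section 9.3: "The analysis for the primary and MRI-based secondary outcomes will be performed on all study completers". The term study completer is not defined.
- **Size endpoint.** Synopsis: "Changes in size of paramagnetic rim lesions at the end of 96 weeks of tolebrutinib 120 mg, relative to non-rim lesions". Section 3: "Changes in size of paramagnetic rim lesions at the end of 96 weeks, relative to non-rim lesions". The T1 row directly above it in Section 3 does name 120 mg.
- **Cohort A.** The synopsis study-population line is "targeting at least 7 participants who complete 48 weeks of therapy with tolebrutinib 60 mg in Cohort A". Section 9.2 has "To recruit 7 study completers in tolebrutinib Cohort A", and its May 2023 update reads "the first 7 participants had completed 48 weeks of tolebrutinib 60 mg, so no additional participants will be recruited into this Cohort". The synopsis study description, 1.2 and 1.3 give Cohort A as 4.

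**The concern.** An analyst working from Section 9 alone meets a population that sounds like 7, a baseline scan that only 4 can have, and no statement linking the two. For size, the undosed Section 3 row adds doubt about window and baseline. The effective sample size of two named secondary endpoints should be visible beside their significance threshold.

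The second issue is the model. Each participant contributes several lesions. If some participants' rim lesions respond and others' do not, lesions within a participant are not independent evidence about the rim effect. Some analyses permitted by 9.4.3 would treat them as if they were, so a result below 0.025 could overstate the evidence for repair. This does not depend on whether n is 4 or 7.

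Finally, baseline to Week 48 is the one window in which all 7 took the same dose, with 7T MRI scheduled at both ends in 1.3. No T1 or size analysis is planned for it.

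**Working it through.** **1. The plan's own figure.** The only sample-size figure in 9.2 belongs to the primary endpoint: the 95% interval for 2 of 7. The exact (Clopper-Pearson) limits are 0.0367 and 0.7096, as stated. No effect size, SD, lesion count or power is given for T1 or size, so there is nothing to reproduce for these tests.

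**2. Number of participants.** Treated: 7 (9.2). Never escalated, hence no pre-120 mg scan: 3 (6.1.2.1). Maximum for 9.4.3: 7 − 3 = 4. Dose reduction does not remove anyone (6.1.2.3), but dropout could.

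**3. Window for size.** Escalation was at Week 48, so 96 weeks of 120 mg ends at 48 + 96 = Week 144, the last fixed Cohort A visit. Read as study Week 96, the undosed Section 3 row would fall after only 96 − 48 = 48 weeks of 120 mg. It would also coincide with a scheduled 7T scan in the 3 participants kept at 60 mg, for whom no baseline scan is named.

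**4. Type I error of a lesion-level ANOVA.** Assumptions: lesion-change variance 1; *a* rim and *b* non-rim lesions per participant; true rim effect zero on average but varying between participants with variance τ² of 0.1 to 0.5; two-sided 0.025 (9.4.3 does not state sidedness). Let h = 1/a + 1/b. Each participant's rim-minus-non-rim change has variance τ² + h. An ANOVA with participant and rim terms only takes it to be roughly h, understating it by a factor of about 1 + τ²/h. Simulated type I error at n=4:

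| Rim + non-rim lesions | h | 1 + τ²/h | Type I error |
|---|---|---|---|
| 1 + 4 | 1.25 | 1.08 to 1.40 | about 0.03 to 0.05 |
| 4 + 10 | 0.35 | 1.29 to 2.43 | 0.045 to 0.13 |
| 8 + 32 | 0.156 | 1.64 to 4.20 | about 0.08 to 0.26 |

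With τ² = 0 and 4 + 10 lesions the ANOVA holds its level (0.024 at n=4). At n=7 with 4 + 10 lesions the range is 0.046 to 0.131, essentially the same. A one-sample t test on one rim-minus-non-rim change per participant stays at 0.024 to 0.026.

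**5. Mixed model without small-sample degrees of freedom.** A Wald z test on participant-level changes has true level 2·P(t with n−1 df > 2.241): 0.111 at n=4 and 0.066 at n=7.

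**6. Precision.** The 95% half-width for a participant-level mean change is t(0.975, n−1)/√n: 3.182/√4 = 1.59 SD at n=4 and 2.447/√7 = 0.92 SD at n=7.

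**The case against.** The strongest reply is that the analysis is not really ambiguous. Sections 9.1 and 9.4.3 tie both endpoints to 120 mg, and a participant who never took 120 mg has no such baseline, so 7 cannot enter. The number 4 is disclosed four times outside Section 9. The Section 3 row omits a dose rather than naming another, and the Cohort A wording in 9.2 is partly historical. All of this stands, and it limits the first part of the point to reconciliation.

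Three stronger readings are tempting but unsupported.

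- A reader might infer that the plan offers two equal definitions, one with 4 and one with 7. It does not, for the reasons just given.
- A reader might see a contradiction between 9.4.2, which pools both cohorts, and 9.4.3, which does not. The primary endpoint is at 60 mg and the secondary ones are at 120 mg, so each is coherent.
- A reader might call low power at n=4 an error. On the participant-level t test, 80% power at two-sided 0.025 needs 2.72 SD at n=4 against 1.49 SD at n=7. But 9.2 claims no power for these tests, the protocol acknowledges the study is small, and the two numbers belong to different doses and windows.

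It is also fair to say that the plan does not specify the additive ANOVA, that any single type I figure depends on an assumed lesion count (entry requires only one rim lesion), and that a 60 mg T1 or size analysis is not owed. Sections 3, 9.4.8 and 9.4.9 leave room for exploratory imaging work. The first two objections are why a range is shown. The last is why the added analysis is proposed as supportive only.

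**Conclusion.** The point holds in two separate parts.

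First, after escalation and recruitment closed, at most 4 participants can enter the T1 and size tests. Section 9 does not say so, and the passages on population, size-endpoint dose label and Cohort A size need to be brought into line. This follows from the text and needs no assumption. The primary analysis is unaffected.

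Second, the open choice of model permits an analysis whose type I error at nominal 0.025 could lie anywhere from about 0.03 to about 0.26. That range assumes rim-effect variance of 0.1 to 0.5 of the lesion variance and the three lesion-count patterns shown. If the rim effect does not vary between participants, there is no inflation. The documents give neither lesion counts nor SDs, so the range is illustrative. A significant result from a suitable participant-level model would be valid even at n=4.

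**What to change.** 1. Reconcile the synopsis, Section 3, 9.2, 9.3 and 9.4.3 on population, dose label, window, baseline scan and Cohort A size. Define study completer for each endpoint, and state n≤4 in 9.4.3.
2. For T1 and size, specify participant-level rim-minus-non-rim changes with a t test, or a mixed model with a participant-level rim effect and a small-sample degrees-of-freedom method. Report the estimate and 95% interval alongside the 0.025 test.
3. Add a supportive T1 and size analysis of all 7 from the pre-tolebrutinib scan to Week 48, using the same model. Label it as added after those data existed (9.2 records all 7 as past Week 48 by May 2023), open-label, and overlapping with anti-CD20 (2.2.5). Make no dose-effect claim from it.

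The cost is protocol wording and one further analysis on scans already scheduled, with no extra visits. The downside is slightly more analysis and a late-specified result that can only be supportive.

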To assess the time course of an effect of tolebrutinib on the paramagnetic rims of chronically inflamed white matter lesions.	Proportion of paramagnetic rim le- sions in which the rim has diminished or disappeared at any time point, as- sessed by analysis of variance or mixed-effects models, which naturally handle missing data.	The time course of any effect of tolebrutinib on chronic neuroinflam- mation is unknown.
To obtain clinical data rele- vant to the efficacy of tole- brutinib.	Expanded Disability Status Scale (EDSS), 9-hole peg test (9HPT), 25- foot timed walk (25FTW), Scripps Neurological Rating Scale (SNRS), and symbol digit modalities test (SDMT), at baseline and every 24 weeks thereafter.	These are standard dis- ability scales that are used in the assessment of clinical progression in MS.
To obtain additional imaging data relevant to the efficacy of tolebrutinib.	Characteristics, including persistence, of paramagnetic rims at all time points (qualitative). Additional MRI measures to be determined. These analyses will be performed in NIH labs or through collaboration, either intramural or extramural.	To assess imaging cor- relates of reduced chronic neuroinflam- mation and/or tissue re- pair.
To obtain laboratory data rel- evant to the safety and effi- cacy of tolebrutinib.	Immune cell populations (e.g., macro- phages, lymphocytes, and subtypes thereof), cytokines (e.g., IL- 1ß, IL-6), and protein and other biomarkers of neuroinflammation and neurodegener- ation (e.g., neurofilament light chain, chitinase-3-like-1). Additional assays may also be developed and performed, such as the rate of repopulation of CD19+ cells. These analyses will be performed in NIH labs or through col- laboration, either intramural or extra- mural.	To assess laboratory correlates of reduced chronic neuroinflam- mation and/or tissue re- pair.

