# 6.1.2 Dosing and Administration

# 6.1.2.1 Dose Escalation

As of January 20, 2023, participants (n=4) who started tolebrutinib 60 mg/day and previously escalated to 120 mg/day† at Week 48 will remain at that dose. Participants (n=3) who initiated tolebrutinib 60 mg/day and did not escalate to 120 mg/day due to the partial clinical hold will be followed on study for an additional 48 weeks, according to the schedule of the Initial Cohort. They will furthermore be eligible to continue taking tolebrutinib 60 mg/day until tolebrutinib becomes FDA-approved or the clinical development program is terminated.

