# 6.1.2.5 Partial Clinical Hold

On June 29, 2022, we were informed by Sanofi that as of June 27, 2022, new enrollment was being halted across all 5 of their US phase 3 trials of tolebrutinib, and that all participants dosed after April 29, 2022 in the US would be required to stop tolebrutinib but would continue for observation on the trials. Sanofi staff detailed a call earlier in the week, on which the FDA verbally communicated a partial clinical hold to the Sponsor. The partial clinical hold was enacted after internal discussions regarding four participants with evidence of drug-induced liver injury (DILI), and the FDA outlined specific steps that Sanofi could take to support lifting the hold.

On July 12, 2022, the FDA issued a partial clinical hold to the NINDS IND as well, with identical stipulations to the Sanofi hold. As such, until the hold is lifted, we will not initiate new subjects on tolebrutinib. However, as no participants in our study had been taking tolebrutinib for less than 60 days at the time of

<sup>† See Section 6.1.2.5

the FDA partial clinical hold, the FDA does not require that we stop tolebrutinib for any participant in our trial. Furthermore, although not specifically stipulated by the FDA, we have elected to defer dose escalation from 60 to 120 mg (the "week 48" time point) until the partial clinical hold is lifted or modified; once the dose is escalated, however, the trial clock will restart.

On January 20, 2023, the FDA requested a revision to the protocol to remove the potential for dose escalation. Participants who have initiated tolebrutinib 60 mg and escalated to 120 mg/day will remain at that dose. The 3 remaining participants who initiated tolebrutinib 60 mg will remain at 60 mg and not be escalated to 120 mg/day.

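### The T1 and lesion-size tests do not make the participant the unit of analysis; with at most 4 participants, some permitted models can exceed the 0.025 error rate

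*Combined protocol and SAP*

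**What the plan says.** For lesion size, Section 9.4.3 states that "changes in size of paramagnetic rim lesions, relative to non-rim lesions, will be determined by analysis of variance or mixed-effects models". For T1 it offers the same pair: "changes in T1 relaxation time within paramagnetic rim lesions, relative to non-rim lesions, will be determined by analysis of variance or" mixed-effects models. Each paragraph closes with the same rule: "A threshold p-value of 0.025 will be taken as a significant change". The Section 3 table repeats the choice for size ("The analysis will be performed by analysis of variance or mixed-effects models") and in similar words for T1.

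The number of people follows from other sections. Section 9.4.3 fixes the reference: "Comparisons are relative to the scan taken just prior to initiation of 120 mg dosing". Section 6.1.2.1 counts those who escalated: "As of January 20, 2023, participants (n=4) who started tolebrutinib 60 mg/day and previously escalated to 120 mg/day". Section 6.1.2.5 closes the door on the others: "The 3 remaining participants who initiated tolebrutinib 60 mg will remain at 60 mg and not be escalated to 120 mg/day". Section 9.3 restricts the MRI secondary outcomes to completers, so 4 is an upper limit. The size row in Section 3 omits the dose, but the synopsis and Sections 9.1 and 9.4.3 all tie the endpoint to 120 mg.

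No section names the unit of analysis, a participant term, random effects, degrees of freedom or sidedness for these tests. Section 9.4.1 (General Approach) is a heading without text, and Section 9 says there is no separate SAP.

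**The concern.** Each participant contributes several rim lesions and usually many more non-rim lesions, all from the same brain, scan sessions and treatment course. The question is whether the rim minus non-rim change generalises across people, so the relevant noise is how far that difference varies from person to person. With 4 people there are 3 degrees of freedom for it, however many lesions are measured.

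The wording covers analyses that respect this and analyses that do not. A reply that the mixed model will be used does not settle it. A participant intercept removes each person's overall level, but leaves person-to-person variation in the rim versus non-rim contrast in the lesion-level error, where it is averaged over lesions instead of people.

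The documents make such variation plausible. Section 2.2.1 links persistent rims to age and to baseline blood cytokine and chemokine profile, which are person-level factors. It also suggests uneven rim counts: entry needs only one rim lesion (Section 5.1.1), while Section 2.2.1 discusses people with 4 or more and one patient with 10 analysed. At stake is whether a p-value below 0.025 can support a statement about possible lesion repair, when the model can still be chosen after the data are seen.

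**Working it through.** **The plan's own figures.** For T1 and size the plan gives no SD, within-person correlation, lesion count or power, so there is nothing to reproduce. The checkable computed figure in Section 9.2 concerns the primary endpoint: the exact (Clopper-Pearson) interval for 2 of 7 is (0.0367, 0.7096), as stated. The two secondary thresholds add to 0.05.

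**Inputs.** From the plan: k = 4 participants; α = 0.025, taken as two-sided because sidedness is not stated. Assumed: m = 4 rim and n = 16 non-rim lesions each (4/20 = 20%, inside the 15–25% quoted in Section 2.2.1). Per-lesion variance is scaled to 1 and split into u (level shared by all lesions of a person), v (participant-by-lesion-type effect, independent for each type) and e = 1 − u − v (lesion error). There is no true rim effect.

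**Step 1: true variance of the contrast.** One person's rim minus non-rim difference has variance 2v + e(1/m + 1/n); u cancels. With u = v = 0.10 and e = 0.80: 0.20 + 0.80 × 0.3125 = 0.45. The mean over 4 people has variance 0.45/4 = 0.1125.

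**Step 2: variance each analysis uses.** Both multiply their residual mean square by 1/16 + 1/64 = 0.0781.
- Lesion-level: expected mean square (80 − 16 × 0.10 − 64 × 0.0625)/78 = 0.954, where 0.10 and 0.0625 are the variances of the overall rim and non-rim means. Variance used: 0.0745.
- Participant block: (72 × 0.80 + 3 × 3.2 × 0.45)/75 = 0.826, with 3.2 = mn/(m + n). Variance used: 0.0645.

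The true variance is 0.1125/0.0745 = 1.51 and 0.1125/0.0645 = 1.74 times what is used. Approximating the rate by 2Φ(−2.24/√ratio) gives 0.068 and 0.090.

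**Step 3: shared level only.** With u = 0.20, v = 0 and e = 0.80, the true variance is 0.80 × 0.3125/4 = 0.0625. The lesion-level analysis still uses 0.0745 (ratio 0.84, rate about 0.014, conservative). The block model uses 0.80 × 0.0781 = 0.0625, which is correct.

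**Step 4: simulation.** At least 20,000 runs per setting for the rows with three decimals; simulation error is about ±0.002 near 0.025. The fixed block stands in for a random intercept.

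| Lesions per person (rim; non-rim) | u | v | Lesion-level ANOVA | Participant block | Participant-level t, 3 df |
|---|---|---|---|---|---|
| 4; 16 | 0.20 | 0 | 0.017 | 0.025 | 0.025 |
| 4; 16 | 0 | 0.10 | 0.070 | 0.077 | 0.024 |
| 4; 16 | 0.10 | 0.10 | 0.068 | 0.087 | 0.024 |
| 1, 2, 4, 9; 20, 15, 12, 10 | 0.30 | 0 | 0.082 | 0.026 | 0.020 |
| 1, 2, 4, 9; 20, 15, 12, 10 | 0.10 | 0.10 | 0.115 | 0.094 | 0.022 |
| 1, 2, 5, 12; 16 each | 0.10 | 0.10 | about 0.13 | about 0.13 | 0.022 |

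Across a wider grid (u to 0.50, v to 0.20, up to 8 rim and 32 non-rim lesions each) the participant-level test ranged from 0.016 to 0.027.

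**Step 5: what 4 people can show.** The two-sided 0.025 critical value on 3 df is 4.18 (3.18 if one-sided), so the 97.5% interval is the mean ± 4.18/√4 = ± 2.09 SD of the participant differences. From the non-central t distribution, two-sided power is about 55% when the mean difference is 2 SD and 87% at 3 SD. An exact sign-flip test cannot reach 0.025: its smallest p-value is 1/16 = 0.0625 one-sided and 2/16 = 0.125 two-sided.

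**The case against.** The strongest reply is that rim versus non-rim is a within-person contrast, so shared person and scanner effects largely cancel, and ignoring them overstates the standard error. This is right when ratios are similar and the contrast does not vary between people; step 3 shows it. A reader might infer that clustering as such always inflates the error rate. It does not.

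Second, the plan nowhere says that the analysis of variance will be at lesion level or will ignore the participant. A repeated-measures analysis of variance on participant means by lesion type is also analysis of variance, is valid, and with two lesion types equals the 3-df test. A reader might conclude that the option should be deleted; that would ban a sound method. What is missing is the unit and the error term.

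Third, these are secondary endpoints in a small open-label study, worded as possible repair, and Sections 9.4.7 and 9.4.8 promise individual descriptions and listings. This limits the harm, but the 0.025 rule remains.

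Fourth, the exploratory row in Section 3 offers "analysis of variance or mixed-effects models, which naturally handle missing data". It is tempting to read this as saying that ordinary analysis of variance handles missing data. The last clause can equally attach to mixed models alone, and Section 9.4.9 leaves exploratory analyses to be defined later, so nothing is built on it.

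**Conclusion.** The point holds in conditional form. The plan permits, but does not prescribe, analyses whose false-positive rate can exceed 0.025. This happens for lesion-level analysis of variance and for intercept-only or block models if the rim versus non-rim contrast differs between people. For lesion-level analysis of variance it also happens if the rim:non-rim ratio differs. Under the stated assumptions the rates are about 0.07 and 0.09 with equal counts, and about 0.13 for both with rim counts 1, 2, 5 and 12. With a shared level only and similar ratios they are 0.017 and 0.025. The participant-level test stays at or below about 0.026, allowing for simulation error.

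The variance split drives these rates: with equal counts, the rise comes from the participant-by-lesion-type part. The documents give no lesion counts, variances or correlations, so a reader should not take any rate as this trial's actual error rate. The limit of 4 people, the open choice of model and the absent unit of analysis come from the plan itself.

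**What to change.** In Section 9.4.3, and to match in Section 3, name one analysis with the participant as the unit. The simplest is each participant's mean change in rim lesions minus mean change in non-rim lesions, tested across participants on 3 df. Repeated-measures analysis of variance on participant means by lesion type is equivalent. The alternative is a mixed model with a random participant-by-lesion-type term and small-sample degrees of freedom, though that may be hard to estimate with 4 people. State whether 0.025 is one- or two-sided. Report the estimate, its interval and the number of participants, not only the number of lesions.

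The change is to wording only and needs no new data. The price is wider intervals and low power (about 55% at a standardised difference of 2). A p-value below 0.025 from 4 people would also lean on the normality assumption, since the sign-flip test cannot reach it. The plan should therefore present these results as largely descriptive, with each participant's difference shown.
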